3.3 Inclusion of Women and Minorities

Both men and women of all races and ethnic groups are eligible for this trial.

4. REGISTRATION PROCEDURES

4.1 General Guidelines for DF/HCC Institutions

Institutions will register eligible participants in the Clinical Trials Management System (CTMS) OnCore. Registrations must occur prior to the initiation of any protocol-specific therapy or intervention. Any participant not registered to the protocol before protocol-specific therapy or intervention begins will be considered ineligible and registration will be denied.

An investigator will confirm eligibility criteria and a member of the study team will complete the protocol-specific eligibility checklist.

Following registration, participants may begin protocol-specific therapy and/or intervention within 7 calendar days. Issues that would cause treatment delays should be discussed with the Overall Principal Investigator (PI). If the subject does not receive protocol therapy following registration, the subject must be taken off-study in the CTMS (OnCore) with an appropriate date and reason entered.

4.1 Registration Process for DF/HCC Institutions

Applicable DF/HCC policy (REGIST-101) must be followed.

4.2 General Guidelines for Other Investigative Sites

Eligible participants will be entered on study centrally at the Dana Farber Cancer Institute by the Study Coordinator. All sites should call the Study Coordinator [contact] to verify availabilities. The required forms will be provided to all external sites by the DFCI study coordination.

Following registration, participants should begin protocol therapy within 7 calendar days. Issues that would cause treatment delays should be discussed with the Overall PI. If the subject does not receive protocol therapy following registration, the subject must be taken off-study in the CTMS (OnCore) with an appropriate date and reason entered. The Study Coordinator should be notified of cancellations as soon as possible.

4.3 Registration Process for Other Investigative Sites

To register a participant, the following documents should be completed by the research nurse or data manager and emailed/faxed to the DFCI Project Manager:

- Signed and dated DFCI eligibility checklist (signed by MD)
- Current IRB approved consent form signed by participant and Investigator (MD only)
- HIPAA authorization form

- External site subject registration form
- The following source documentation is typically required:
 - Documentation of prior treatments/procedures performed to treat RCC
 - Reports documenting disease status
 - MRI or CT Brain
 - Chest CT
 - CT or MRI Abdomen and Pelvis
 - Bone Scan if applicable
 - Pathology Report
 - Concomitant medication list
 - Progress note or equivalent documentation of consenting visit
 - Progress note documenting medical history and oncologic history
 - Screening Labs
 - Complete blood count with differential
 - Electrolytes
 - Liver Function Tests
 - Urinalysis
 - Coagulation factors
 - Pregnancy test
 - Viral serologies (HBV, HCV, HIV)
 - Screening visit note with vital signs, weight, height, ECOG performance status, physical examination
 - Screening ECG, ECHO

The participating site will then call [contact] or e-mail the Study Coordinator to verify eligibility. The Study Coordinator will follow DF/HCC policy (REGIST-101) and register the participant on the protocol. The Study Coordinator will fax or e-mail the participant study number, and if applicable the dose treatment level, to the participating site. The Study Coordinator will also contact the participating site and verbally confirm registration

5. TREATMENT PLAN

5.1 Treatment Regimen

For patients enrolled in arm 1, abemaciclib single-agent will be administered orally, twice daily, at a starting dose of 200mg bid, on days 1 to 28 of a 28-day cycle as described in **Table 1**. Reported adverse events and potential risks are described in Section 7. Appropriate dose modifications are described in Section 6.

Arm 2 consist in a standard 3+3 dose escalation scheme with two planed dose levels of abemaciclib, 100mg bid and 150mg bid, in association with MK-6482 at the dose of 120mg qd, as described in **Table 2** and **Table 3**. MTD is defined as the highest dose studied at which no more than 1 of 6 subjects has experienced a DLT in cycle 1. If only three patients are treated at the MTD, an additional three patients will be added for a total of six patients at the MTD. The dose will be escalated either until an MTD is identified or the maximum planned dose is achieved.

Participants will be continued on therapy until radiographic progression or withdrawal for other reason as detailed in section 5.6.

No investigational or commercial agents or therapies other than those described below may be administered with the intent to treat the participant's malignancy.

Table 1. Regimen description in Arm 1.

Arm 1: Regimen Description					
Agent	Premedications; Precautions	Dose	Route	Schedule	Cycle Length
Abemaciclib	None	200mg	PO	Every 12 hours	28 days (4 weeks)

Table 2. Dose escalation schedule in Arm 2.

Dose Escalation Schedule		
Dose Level	Dose	
	Abemaciclib	MK-6482
Level 1- Starting Dose	100mg bid	120mg daily
Level 2	150mg bid	120mg daily

Table 3. Regimen Description in Arm 2.

Arm 2: Regimen Description					
Agent	Premedications; Precautions	Dose	Route	Schedule	Cycle Length
Abemaciclib	None	See dose escalation schedule	PO	Every 12 hours	28 days (4 weeks)
MK-6482	Fasting⁽¹⁾	120mg	PO	Every 24 hours	

⁽¹⁾ MK-6482 should be taken in the morning at least 2 hours after the last meal and patients should refrain from eating for at least 1 hour after taking each dose. Should be taken in the morning and can take with abemaciclib.

The participant will be requested to maintain a medication diary of each dose of medication. The medication diary will be returned to clinic staff at the end of each cycle.

5.2 Pre-Treatment Criteria

5.2.1 Cycle 1, Day 1

Patients should meet the clinical requirements for eligibility criteria at cycle 1 day 1. The following laboratory parameters should be met:

- ANC \geq 1,500 mcL
- platelet count \geq 100,000/uL
- hemoglobin \geq 10 g/dL (transfusions allowed)
- total bilirubin \leq 2.0 x institutional upper limit of normal with the following exception: patients with known Gilbert disease should have a serum bilirubin \leq 3 x ULN
- AST(SGOT)/ALT(SGPT) \leq 3 x institutional upper limit of normal with the following exception: patients with known liver metastases should have AST and ALT \leq 5 x ULN
- creatinine clearance \geq 30 mL/min/1.73 m² according to the Cockcroft-Gault formula

5.2.2 Subsequent Cycles

Labs should be reviewed and toxicities should be assessed prior to therapy.

5.3 Agent Administration

5.3.1 Abemaciclib

Abemaciclib will be supplied as tablets for oral administration. The tablets should be stored at room temperature according to the range provided on the product label and not crushed, chewed or dissolved. Investigators should instruct patients to store the tablets in the original package and in a location inaccessible to children.

Abemaciclib will be taken orally every 12 (\pm 2) hours on Days 1 through 28 of a 28-day cycle, for a total of 56 doses per cycle. During all cycles, abemaciclib should be taken at approximately the same times each day. If a patient misses or vomits a dose, that dose should be omitted.

5.3.2 MK-6482

MK-6482 will be supplied as tablets for oral administration. MK-6482 should not be crushed, chewed or dissolved in water. MK-6482 must be stored in a secure location in accordance with the study drug label.

MK-6482 will be taken orally every approximately 24 hours on Days 1 through 28 of a 28-day cycle, for a total of 28 doses per cycle. Patients should not consume food beginning 2 hours before and ending 1 hour after taking MK-6482. During all cycles, MK-6482 should be taken at approximately the same times each day. Missed doses of MK-6482 may be made up if taken within 12 hours after the scheduled administration time. Patients who vomit after study drug administration should not retake that study drug dose but should resume taking study drug at the next scheduled administration time.

5.4 Definition of Dose-limiting Toxicity

For patients treated in arm 2, DLT will be defined as any abemaciclib or MK-6482 related toxicity resulting in discontinuation or dose reduction per the guidelines in the Section 6.2 to 6.87 within the first 28 days of treatment, for which there is no clear alternative explanation (i.e. disease related).

DLTs will be defined as any of the following events not clearly due to the underlying disease or extraneous causes:

- Any death
- Non-hematologic toxicity:
 - Grade 3 or higher
 - Hy's law cases
- Hematologic toxicity (for non-acute leukemia indications):
 - Grade 4 neutropenia for more than 7 days
 - Grade 3 or higher thrombocytopenia with clinically significant bleeding
 - Neutropenic fever

The DLT definition may exclude:

- Grade 3 nausea/vomiting or diarrhea for less than 72 hours with adequate antiemetic and other supportive care
- Grade 3 or higher electrolyte abnormality that lasts up to 72 hours, is not clinically complicated, and resolves spontaneously or responds to conventional medical interventions
- Grade 3 or higher amylase or lipase that is not associated with symptoms or clinical manifestations of pancreatitis

Patients within arm 2 who do not receive at least 80% of the intended abemaciclib plus MK-6482 doses during the first 28 days for reasons other than toxicity, will not be evaluable for DLTs and will be replaced. Once a tolerable dose combination has been determined in arm 2, patients will no longer be replaced in the study.

Dose escalation will proceed within each cohort according to **Table 4**. Dose-limiting toxicity (DLT) is defined above.

Table 4. Dose-escalation scheme

Number of Participants with DLT at a Given Dose Level	Escalation Decision Rule
0 out of 3	Enter 3 participants at the next dose level.
≥ 2	Dose escalation will be stopped. This dose level will be declared the maximally administered dose (highest dose administered). Three (3) additional participants will be entered at the next lowest dose level if only 3 participants were treated previously at that dose.
1 out of 3	Enter at least 3 more participants at this dose level. 
 • If 0 of these 3 participants experience DLT, proceed to the next dose level. • If 1 or more of this group suffer DLT, then dose escalation is stopped, and this dose is declared the maximally administered dose. Three (3) additional participants will be entered at the next lowest dose level if only 3 participants were treated previously at that dose.
≤ 1 out of 6 at highest dose level below the maximally administered dose	This is generally the recommended phase 2 dose. At least 6 participants must be entered at the recommended phase 2 dose.

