6.2 General guidelines for dose delays and dose modifications

General guidelines for dose reductions and delays according to non-laboratory and laboratory adverse events are summarized in **Table 7** and **Table 8**, respectively. Hematologic adverse events, thrombotic adverse events, diarrhea, nausea, vomiting, liver function tests and serum creatinine abnormalities are subject to specific guidelines described in the following sections.

In the situation where an adverse event is thought to be related to both study drugs (abemaciclib, MK-6482) in arm 2, recommendation for the management of toxicities related to all study drugs should apply. In the situation where an adverse event requiring is considered related only to abemaciclib or MK-6482 in arm 2, recommendation for the management of toxicities related only to abemaciclib or MK-6482 may apply. If a patient requires omission of more than 25% of doses for one or both study drugs during a cycle for tolerability, then treatment may continue if the investigator determines the patient is receiving clinical benefit.

A cycle is defined as the planned treatment interval of 28 days plus any subsequent delay prior to start of the next cycle. A delay in the start of a cycle due to holidays, weekends, bad weather, or other unforeseen circumstances will be permitted up to 7 days and not counted as a protocol deviation. Dose omissions are allowed within a cycle. Imaging evaluations should continue on schedule regardless of treatment delays or interruptions.

Table 7. General guidelines for dose adjustments and delays related to non-laboratory toxicities in patients treated with abemaciclib and abemaciclib plus MK-6482. These guidelines do not apply to the management of thrombotic adverse events, diarrhea, nausea, and vomiting, interstitial lung disease/pneumonitis which are subject to specific guidelines reported within following sections.

Treatment Related Toxicity	Arm 1 – abemaciclib alone	Arm 2 – Abemaciclib plus MK-6482
Grade 2 toxicity > 7 days not resolving despite appropriate symptomatic treatment	Hold abemaciclib until resolution of toxicity to baseline or grade 1.	Hold abemaciclib and/or MK-6482 until resolution of toxicity to baseline or grade 1.
Grade 3 toxicity	Hold abemaciclib until resolution of toxicity to baseline or grade 1.	Hold abemaciclib and/or MK-6482 until resolution of toxicity to baseline

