Recurrent grade 3 Grade 3 thrombocytopenia with bleeding Grade 3 neutropenia with body temperature \geq 38.5°C	Hold abemaciclib until resolution of toxicity or grade 2. Abemaciclib dose must be reduced by one dose level.	Hold abemaciclib and/or MK-6482 until resolution of toxicity to grade 2. Abemaciclib dose must be reduced by one dose level. Resume MK-6482 at lower dose level.
Grade 4		

Table 9b General guidelines for dose adjustments and delays related to anemia in patients treated with abemaciclib and abemaciclib plus MK-6482.

Toxicity	Arm 1 – abemaciclib alone	Arm 2 – Abemaciclib plus MK-6482

Grade 3	Hold abemaciclib until resolution of toxicity to grade 2.	Hold abemaciclib and/or MK-6482 until resolution of toxicity to grade 2.
Grade 4	
Hold abemaciclib until resolution of toxicity to grade 2.
 
Transfusion and/or ESA support
 
Abemaciclib dose must be reduced by one dose level.
	
Hold abemaciclib and/or MK-6482 until resolution of toxicity to grade 2.
 
Transfusion and/or ESA support
 
Abemaciclib dose must be reduced by one dose level.
 
Resume MK-6482 at lower dose level.

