Grade 2 > 24 hours despite appropriate supportive measures	Hold abemaciclib until resolution of toxicity or grade 1. Abemaciclib dose may be reduced by one dose level, at investigator discretion	Hold abemaciclib and MK-6482 until resolution of toxicity to grade 1. Abemaciclib dose may be reduced by one dose level, at investigator discretion Resume MK-6482 at lower dose level.
Any grade requiring hospitalization and/or IV fluids. Recurrent grade 2 despite appropriate supportive measures. Grade 3 or 4.	Hold abemaciclib until resolution of toxicity or grade 1. Abemaciclib dose must be reduced by one dose level.	Hold abemaciclib and MK-6482 until resolution of toxicity to grade 1. Abemaciclib dose must be reduced by one dose level. Resume MK-6482 at lower dose level.

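### Section 5.4 defines arm 2 DLT twice, in ways that disagree in both directions, and adds optional exclusions, so the DLT count behind the co-primary MTD is not unique

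*Combined protocol and SAP*

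**What the plan says.** Section 5.4 has three parts.

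- **Action-based definition.** A DLT is "any abemaciclib or MK-6482 related toxicity resulting in discontinuation or dose reduction per the guidelines in the Section 6.2 to 6.87". The event must fall in the first 28 days and have no clear alternative explanation. The cross-reference runs past the end of Section 6, whose last subsection is 6.8.
- **Event list.** The next paragraph begins "DLTs will be defined as any of the following events not clearly due to the underlying disease or extraneous causes". It lists any death; grade 3 or higher non-hematologic toxicity and Hy's law cases; and three hematologic events (grade 4 neutropenia beyond 7 days, grade 3 or higher thrombocytopenia with clinically significant bleeding, and neutropenic fever).
- **Exclusions.** "The DLT definition may exclude" three kinds of event. One is "Grade 3 nausea/vomiting or diarrhea for less than 72 hours with adequate antiemetic and other supportive care". No criterion and no decision-maker is given.

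The lead-in to Table 4 says only that DLT has been defined above. Sections 5.1, 14.1.1 and 14.3.3 use the DLT count (at most 1 of 6 in cycle 1) without defining DLT again. Section 6.2 adds that when an event is attributed to one drug, "recommendation for the management of toxicities related only to abemaciclib or MK-6482 may apply".

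**The concern.** The MTD rule is stated consistently, but it needs a count, and Section 5.4 does not produce a single count. An investigator using the action-based paragraph and one using the list could classify the same cycle 1 events differently, and both would be following the protocol.

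The MTD is a co-primary endpoint in arm 2. It also decides which dose is expanded to 20 patients for the other co-primary endpoint, the response rate. Only two dose levels are planned, so one changed decision can change the declared MTD. If the definition is chosen after events have been seen, that choice depends on the data.

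**Working it through.** **1. The plan's own figures.** The plan gives no DLT rate and no operating characteristics for the 3+3, so there is none to reproduce. The enrollment that follows from the cohorts does reproduce: 3 or 6 patients at the other level plus 20 at the MTD is 23 or 26, and 11 + 26 = 37 (Section 14.2).

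**2. Events classified under each definition** (arm 2 columns of Section 6):

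| Cycle 1 event | Section 6 action | Action-based | List |
|---|---|---|---|
| Grade 4 anemia (Table 9b) | "Abemaciclib dose must be reduced by one dose level"; MK-6482 resumed lower | DLT | not listed |
| Grade 2 AST/ALT beyond 7 days despite maximal support (Table 11) | both drugs resumed lower | DLT | not listed |
| Grade 2 pneumonitis not resolving within 7 days despite maximal support (Table 13) | both drugs resumed lower | DLT | not listed |
| Diarrhea, nausea or vomiting, "Grade 2 > 24 hours despite appropriate supportive measures" (Table 10) | MK-6482 resumed lower; abemaciclib reduction discretionary | DLT, unless attributed to abemaciclib alone and not reduced | not listed |
| Isolated grade 3 AST/ALT resolving within 48 h, no bilirubin criterion (Table 11) | none; the row starts beyond 48 h | not a DLT | DLT |
| Grade 3 diarrhea or vomiting under 72 h (Table 10 row ending "Recurrent grade 2 despite appropriate supportive measures. Grade 3 or 4") | both drugs lowered | DLT | DLT, or not if the exclusion is used |

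The first three rows lower both drugs, so attributing the event to one drug does not remove the disagreement. Rows 1 to 4 and row 5 disagree in opposite directions.

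**3. Decisions that change.**

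- Three patients, two with grade 2 diarrhea beyond 24 h despite support, attributed to both drugs: 2/3 under the action-based definition (stop), 0/3 under the list (escalate).
- Six patients, one with grade 4 anemia and one with 48 h of grade 3 diarrhea: 2/6 under the action-based definition (fails). Under the list it is 1/6, or 0/6 if the exclusion is used (passes either way).
- Six patients, two with isolated grade 3 AST/ALT resolved within 48 h: 0/6 under the action-based definition (passes), 2/6 under the list (fails).

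**4. Size, under assumed rates.** With DLT probability p and q = 1 − p, a level clears the 3+3 step at 0/3, or at 1/3 followed by 0/3:

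P(clear) = q³ + 3pq² × q³

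| p | 0.05 | 0.10 | 0.15 | 0.20 | 0.25 | 0.30 |
|---|---|---|---|---|---|---|
| P(clear) | 0.973 | 0.906 | 0.814 | 0.709 | 0.600 | 0.494 |
| P(at most 1 of 6) = q⁶ + 6pq⁵ | 0.967 | 0.886 | 0.776 | 0.655 | 0.534 | 0.420 |

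Let b be the share of patients with a DLT under both definitions, and d the further share counted by only one. If the disputed events all run one way, the probability of opposite results in the same patients is P(clear at b) − P(clear at b + d). For b = d = 0.10 this is 0.9061 − 0.7086 = 0.198. Over b = 0.05 to 0.20:

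| d | Opposite result, 3+3 step | Opposite result, at most 1 of 6 |
|---|---|---|
| 0.05 | 0.07–0.11 | 0.08–0.12 |
| 0.10 | 0.16–0.21 | 0.19–0.24 |
| 0.15 | 0.26–0.32 | 0.31–0.36 |

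Two-way case, 10% agreed and 5% disputed each way (so 80% with neither and a rate of 0.15 under each definition): P(both clear) = 0.8³ + 2 × (3 × 0.05 × 0.8²) × 0.85³ + (3 × 0.10 × 0.8² + 6 × 0.05 × 0.05 × 0.8) × 0.8³ = 0.512 + 0.118 + 0.104 = 0.734. P(opposite results) = 2 × (0.8138 − 0.7344) = 0.159.

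The diarrhea rates in Section 7.1.1 (90% any grade, 20% grade 3) are for abemaciclib alone. They give no grade 2 share, duration or cycle, so they do not fix b or d.

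**The case against.** The best defense is that neither paragraph says only. Each can be read as sufficient, and Table 4 refers to one definition, so the two together form a union. On that reading, every event in rows 1 to 3 and row 5 is a DLT, as is row 4 when a reduction follows, and those conflicts disappear. The exclusion sentence also speaks of the definition in the singular, so it could carve short grade 3 gastrointestinal events out of both paragraphs.

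This is a possible reading, but it is not written. A reading that requires both paragraphs to be met is no less available, and it gives different counts: grade 4 anemia is a DLT under the union and not under the intersection. Even under the union, the word may leaves the exclusions undecided.

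Three narrower points have some force. The grade 2 rows apply only after adequate supportive care, so those events are rarer than their grade alone suggests; rows 1 and 5 carry no such condition. The 3+3 step formula describes clearing a level, whereas declaring the MTD needs at most 1 of 6; that stricter rule gives larger disagreement, not smaller. The faulty cross-reference changes no count by itself.

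The PI safety evaluation (Section 14.3.3) and the DSMC review (Section 13.1.3) allow case-by-case judgment, but neither says which definition is counted.

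**Conclusion.** The concern holds. Section 5.4 gives two definitions that overlap without either containing the other, and a set of exclusions with no rule for their use. The same patients can produce opposite escalation and MTD decisions, in either direction. This follows from the text and the Section 6 tables and needs no assumed rate.

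The probabilities do rest on assumed rates: with 5 to 20% agreed DLTs and 5 to 15% disputed, opposite results occur with probability 0.07 to 0.32 for the 3+3 step and 0.08 to 0.36 for the at-most-1-of-6 rule. Because the count drives a co-primary endpoint and the expansion dose, this must be fixed before arm 2 is evaluated.

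**What to change.** Before the first arm 2 cohort is evaluated:

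- Replace the two paragraphs of Section 5.4 with one DLT definition, checked row by row against Tables 7 to 13, so that every event there is plainly a DLT or not. Which definition governs is for the sponsor to decide.
- For each event in the exclusion list, state whether it is or is not a DLT, and reconcile the short grade 3 gastrointestinal events with Table 10.
- Say how attribution to one drug affects the count.
- Correct the Section 6 cross-reference.
- Have Sections 5.1, 14.1.1 and 14.3.3 refer to that single definition.

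The cost is a protocol amendment with IRB review. No patients or procedures are added.

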5.5 General Concomitant Medication and Supportive Care Guidelines

Concomitant medication is defined any medication, over-the-counter preparation, or alternative therapies used within 7 days prior to the screening evaluation and prior to the last study visit. All concomitant medications administered within 14 days prior to Cycle 1, Day 1 and during the study until last study visit will be collected on study-specific electronic Case-Report Forms (eCRFs). The reason(s) for treatment and dates of treatment should be reported to the investigator and recorded as instructed on the study-specific eCRFs.

The Overall PI should be alerted if the participant is taking any agent known to affect or with the potential to affect selected CYP450 isoenzymes. **Appendix B** presents guidelines for identifying medications/substances that could potentially interact with the study agent(s).

